5. SUBJECT ENROLLMENT

Before subjects begin participation in any study-specific activities/procedures, Amgen requires a copy of the site's written institutional review board/independent ethics committee (IRB/IEC) approval of the protocol, informed consent form, and all other subject information and/or recruitment material, if applicable (see [Section 11.2](#)). All subjects must personally sign and date the informed consent form before commencement of study-specific activities/procedures. **Screening is initiated from the time of obtaining informed consent. The screening period must be completed within 28 days.**

A subject is considered enrolled upon randomization. The investigator is to document and date this decision in the subject's medical record and on the enrollment **electronic case report form (eCRF)**.

Each subject who enters into the screening period for the study upon signing informed consent receives a unique subject identification number before any study-related activities/procedures are performed. The subject identification number will be assigned through an interactive voice/web response system (IVRS/IWRS). This number will be used to identify the subject throughout the clinical study and must be used on all study documentation related to that subject. Subjects who do not meet LDL-C eligibility criteria cannot be rescreened.

The subject identification number must remain constant throughout the entire clinical study; it must not be changed after initial assignment, including if a subject is rescreened. This number will not necessarily be the same as the randomization number assigned for the study. PPD [REDACTED]

[REDACTED]

[REDACTED]

[REDACTED]

[REDACTED]

5.1 Randomization/Treatment Assignment

Subjects will be randomized 2:2:1:1 assignment to 4 treatment groups and will be based on a computer-generated randomization schedule prepared by Amgen before the start of the study. Randomization will be stratified by screening LDL-C concentration (< 180 mg/dL [4.66 mmol/L] vs. ≥ 180 mg/dL) and baseline **statin use**.

The following are treatment groups (2:2:1:1 respectively):

- Evolocumab SC, 420mg QM (3 AI/Pen or one Personal Injector) and PO placebo 10mg QD
- Evolocumab SC, 140mg Q2W (1 AI/Pen) and PO placebo 10mg QD
- Placebo SC 420mg QM (3 AI/Pen or one Personal Injector) and PO ezetimibe 10mg QD
- Placebo SC 140mg Q2W (1 AI/Pen) and PO ezetimibe 10mg QD

Once eligibility into the study has been confirmed, a site representative will make the randomization call to the IVRS/IWRS to assign a randomization number to the subject. The randomization call to the IVRS/IWRS is accomplished by entering the pertinent information detailed in the IVRS/IWRS user manual. A confirmation **email** will be sent to the site to verify that the correct information has been entered and to confirm the assignment of a randomization number. A subject will be considered randomized when a corresponding randomization number is assigned.

Please refer to [Section 5.2](#) below for details on when and how the randomization code may be broken. The treatment assignment date is to be documented in the subject's medical record and on the enrollment eCRF.

5.2 Site Personnel Access to Individual Treatment Assignments

A subject's treatment assignment should only be unblinded when knowledge of the treatment is essential for the further management of the subject on this study. Unblinding at the study site for any other reason will be considered a protocol deviation.

Refer to the IVRS/IWRS manual for instructions on unblinding.

The investigator is strongly encouraged to contact the Amgen Clinical Study Manager before unblinding any subject's treatment assignment, but must do so within 1 working day after the event.

6. TREATMENT PROCEDURES

Evolocumab (AMG 145), placebo SC, ezetimibe PO, and placebo PO are IPs in this study. An Investigational Product Instruction Manual (IPIM) containing detailed information regarding the storage, preparation, **destruction**, and administration of IP will be provided separately.

6.1 Classification of Product(s) and/or Medical Device(s)

The Amgen Investigational Product(s) and/or matched placebo (except if required by local regulation) used in this study include(s): SC evolocumab (AMG 145) and SC Placebo.

The Non-Amgen investigational product(s) used in this study include: PO Ezetimibe 10 mg, and PO Placebo.

The Investigational Product Instruction Manual (IPIM), a document external to this protocol, contains detailed information regarding the storage, preparation, **destruction**, and administration of evolocumab, matched placebo, and over-encapsulated ezetimibe.

The medical device(s) used in this study include(s): Prefilled AI/Pen and Personal Injector.

6.2 Investigational Product

6.2.1 Amgen Investigational Product Evolocumab (AMG 145)

Evolocumab and respective placebo will be manufactured and packaged by Amgen Inc. and distributed using Amgen clinical IP distribution procedures.

Evolocumab will be presented as a sterile, preservative-free solution in a single use, disposable, handheld mechanical (spring-based) 1.0 mL prefilled autoinjector/pen (AI/Pen) or 3.5 mL Personal Injector for fixed dose, subcutaneous injection. The prefilled AI/Pen contains a 1.0 mL deliverable volume of 140 mg/mL evolocumab.

The Personal Injector with prefilled cartridge assembly is a single-use, disposable, on-body electro-mechanical injection device that is co-packaged with a prefilled Crystal Zenith (CZ) cartridge assembly containing 3.5 mL deliverable volume of 120 mg/mL evolocumab.

Evolocumab should be stored protected from light and according to the storage and expiration information (where required) provided on the label. Evolocumab should be handled per the instructions provided in the IPIM. AI/Pens should be checked for cracks or damage that may occur during shipment or if not handled properly. Damaged product should not be administered. Further details are provided in the IPIM.

The box number of IP (active drug or placebo) is to be recorded on each subject's Drug Administration eCRF.

6.2.1.1 Dosage, Administration, and Schedule

IP will be administered SC (evolocumab or matched placebo) in accordance with instructions in the IPIM. **For visits with IP administration at the study site, administration should be the last procedure to be performed during each visit.** The date and time of evolocumab or placebo will be recorded on the individual subject's worksheet and eCRF. After **the first** IP administration at **the first** dosing visit, subjects should be observed for at least 30 minutes before being discharged.

Details of preparing and administering IP are included in the IPIM provided by Amgen at the start of the study. The dosing schedule is described by a [schema](#) in the protocol synopsis.

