2.4 Rationale

There is an established unmet medical need in Japan for patients with hypercholesterolemia who experience muscle-related side effects when using statins. Amgen is therefore seeking an indication for the use of evolocumab alone or in combination with a statin or other lipid-lowering therapies in patients with hypercholesterolemia who are statin-intolerant or unable to tolerate an effective dose of a statin.

Subjects on low or atypical statin therapy must be on a stable dose for at least 4 weeks prior to screening and throughout the blinded portion of the study; the dose cannot be adjusted during screening and for the duration of the study.

This design provides a scientifically rigorous study to show the superiority of evolocumab over ezetimibe in Japanese patients who are intolerant to statins. Identified patients will be randomized 2:2:1:1 to QM evolocumab + PO placebo **each day (QD), every 2 weeks (Q2W)** evolocumab + PO placebo QD, QM SC placebo + ezetimibe QD, or Q2W SC placebo + ezetimibe QD for a head to head comparison evolocumab versus ezetimibe.

Long term exposure data will be provided by a 9-month open label extension where all patients will receive evolocumab in the same SC regimen (QM or Q2W) they were randomized to on Day 1.

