- b. Acceptable methods of preventing pregnancy include not having intercourse (sexual abstinence), surgical contraceptive methods – (vasectomy of the male partner **[and testing shows there is no sperm in the semen]** or bilateral tubal ligation/occlusion), or use of hormonal birth control methods (pills, patches), intrauterine devices (IUDs), **intrauterine hormonal-releasing system (IUS), male partner uses a condom with or without spermicide, use of a cervical cap, diaphragm, or contraceptive sponge with spermicide**; or two (2) barrier methods (each partner must use one barrier method) with spermicide – males must use condom with spermicide; females must choose either diaphragm with spermicide, OR cervical cap with spermicide, OR contraceptive sponge with spermicide.
- c. Note: If additional medications are given during treatment which may alter the contraceptive requirements (these additional medications may require an increase in the number of contraceptive methods and/or length of time that contraception is to be utilized **and/or length of time breastfeeding is to be avoided** after the last dose of protocol-required therapies) the investigator is to discuss changes with the study subject.

- 220 Subject who is pregnant or breast feeding, or planning to become pregnant or breastfeed during treatment with SC IP (evolocumab/placebo) and/or within 15 weeks after the end of treatment with SC IP (evolocumab/placebo)
- 221 Subject who has previously received evolocumab or any other therapy to inhibit PCSK9
- 222 Subject who has any kind of disorder that, in the opinion of the investigator, may compromise the ability of the subject to give written informed consent and/or to comply with all required study procedures
- 223 Malignancy except non-melanoma skin cancers, cervical or breast ductal carcinoma in situ within the last 5 years
- 224 Subject who has known sensitivity **or intolerance** (eg, allergy or serious adverse reaction to ezetimibe) to any of the products or components to be administered during dosing
- 225 Subject who is likely to not be available to complete all protocol-required study visits or procedures, and/or to comply with all required study procedures (eg, Patient Reported Outcomes [PROs]) to the best of the subject and investigator's knowledge

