- SF-36
- Central Laboratory Assessments as Per Schedule of Assessments
- **Urine pregnancy test (for female subjects of childbearing potential only): precedes on-site SC IP administration**
- PO IP tablet count
- SC IP dispensing (subjects will continue with the previously assigned dosing regimen of Q2W or QM)
- Remind patients to discontinue blinded oral IP
- SC IP administration on-site (all subjects)

7.2.3.8 Visit/Week 24

The following procedures will need to be conducted at this visit for all subjects unless specified otherwise (± 3 days).

- Vital signs (eg, sitting blood pressure, heart rate, respiratory rate, temperature)
- Review for **adverse events**, **serious adverse events**, **and adverse device effects**
- Documentation of concomitant medications
- Central Laboratory Assessments as Per Schedule of Assessments
- SC IP dispensing (subjects will continue with the previously assigned dosing regimen of Q2W or QM)

7.2.3.9 Visit/Week 36

The following procedures will need to be conducted at this visit for all subjects unless specified otherwise (± 3 days).

- Vital signs (eg, sitting blood pressure, heart rate, respiratory rate, temperature)
- Review for **adverse events**, **serious adverse events**, **and adverse device effects**
- Documentation of concomitant medications
- Central Laboratory Assessments as Per Schedule of Assessments
- SC IP dispensing (subjects will continue with the previously assigned dosing regimen of Q2W or QM)

7.2.3.10 Visit/Week 48

The following procedures will need to be conducted at this visit for all subjects unless specified otherwise (± 3 days).

- Vital signs (eg, sitting blood pressure, heart rate, respiratory rate, temperature)
- Review for **adverse events**, **serious adverse events**, **and adverse device effects**
- Documentation of concomitant medications
- Central Laboratory Assessments as Per Schedule of Assessments
- SC IP dispensing (subjects will continue with the previously assigned dosing regimen of Q2W or QM)

7.2.3.11 Visit/Week 52

The following procedures will need to be conducted at this visit for all subjects unless specified otherwise (± 3 days).

- Vital signs (eg, sitting blood pressure, heart rate, respiratory rate, temperature)
- Review for **adverse events**, **serious adverse events**, **and adverse device effects**
- Documentation of concomitant medications
- Physical exam

- Body weight and waist circumference
- Central Laboratory Assessments as Per Schedule of Assessments

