10.2 Sample Size Considerations

The planned sample size for the comparison between evolocumab and ezetimibe is 40 (20 in Q2W and QM each) and 20 subjects (10 in Q2W and QM each), respectively (60 total). The primary analysis will require the 2-sided tests of each co-primary endpoint to be significant at a level of 0.05. From the global phase 3 study 20110116, the treatment effect of evolocumab compared to ezetimibe for reduction from baseline in LDL-C at week 12 is at least 37.6% (32.9%, 42.2%) and for the mean of week 10 and 12, 36.9% (31.6%, 42.3%). Assuming 5% of randomized subjects do not receive any IP and with a common standard deviation (SD) of approximately 20%, this study has at least 93% power to detect a treatment effect of 20% or greater reduction for each of the co-primary endpoints in testing the superiority of evolocumab over ezetimibe, based on a two-sided t-test with significance level 0.05.

As the co-primary endpoints are correlated, there is at least 85% (93% x 93%) power to detect significant treatment effects of the co-primary endpoints. The power calculation is derived using nQuery version 7.01.

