10.4.2 Primary Analysis

To evaluate efficacy and safety of 12 weeks of evolocumab compared with ezetimibe **and summarize 12 weeks of data from the open-label extension (weeks 12 to 24)**, the primary analysis will be performed when all the randomized subjects in the study have either completed the scheduled visits up to and including Week **24** or have early terminated from the study. At that time, the database of the study will be cleaned, processed and a snapshot will be taken; the study will also be unblinded.

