Appendix B. Analytical Study Week Assignments

Selected endpoints will be summarized by scheduled study visits in descriptive analyses.

Since the actual visits may not exactly coincide with their scheduled visit day, the actual visit day is mapped to the study visit generally by non-overlapping consecutive intervals covering the entire time continuum. The mapping intervals for all distinct schedules are summarized in the following tables.

Scheduled Visit Week	Week 2	Week 8	Week 10	Week 12	Week 24	Week 36	Week 48	Week 52	Week 54 EOS Phone Call
Scheduled Visit Day	15	57	71	85	169	253	337	365	379
Vital Signs		(1, 63]	(63, 77]	(77, min(91, first dose date of OLE)]	(min(91, first dose date of OLE), 210]	(210,294]	(294,350]	>350	
Fasting Lipids	(1, 35]	(35, 63]	(63, 77]	(77, min(91, first dose date of OLE)]	(min(91, first dose date of OLE), 210]	(210,294]	(294,350]	(350,378]	
Lp(a), ApoA1, ApoB			(1, 77]	(77, min(91, first dose date of OLE)]	(min(91, first dose date of OLE), 210]	(210,294]	(294,350]	(350,378]	
PK, PCSK9	(1, 42]		(42, 77]	(77, min(91, first dose date of OLE)]				(min(91, first dose date of OLE), 378]	
Hematology and Chemistry		(1, 70]		(70, min(91, first dose date of OLE)]				> min(91, first dose date of OLE)	
Physical Exam, hsCRP, Urinalysis, HbA1c, Biomarkers, anti-evolocumab antibodies				(1, min(91, first dose date of OLE)]				> min(91, first dose date of OLE)	
Weight, waist circumference								> 1	

Handling multiple records assigned to an analytical study week:

If there is more than one record in a study week interval, the analytical record for that specific study week will be defined as the record closest to the scheduled visit day of that specific study week ($7 \times$ study week + 1). If two records are equidistant from the scheduled day, then the earlier record will be chosen. If there are multiple records on the same day, the last record will be used.

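### The 30-minute observation covers only Day 1, when the ezetimibe groups get SC placebo, so up to 20 of 60 subjects have no stated observation after their first evolocumab dose

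*Protocol*

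**What the plan says.** Protocol 6.2.1.1 attaches the observation to the first administration at the first "dosing visit, subjects should be observed for at least 30 minutes before being discharged". The Amendment 3 rationale lists the restriction to the first IP administration visit as an intended change. That visit is Day 1 (7.2.3.1), when SC IP is given on site to everyone.

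For the control groups the Day 1 injection contains no evolocumab. Protocol 5.1 describes one of them as "Placebo SC 140mg Q2W (1 AI/Pen) and PO ezetimibe 10mg QD", and the QM control group likewise receives SC placebo. Earlier exposure is excluded by criterion 221: "Subject who has previously received evolocumab or any other therapy to inhibit PCSK9".

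Protocol 2.4 then describes an "open label extension where all patients will receive evolocumab in the same SC regimen". At Week 12 (7.2.3.7) subjects are reminded to stop oral IP, and the list includes "SC IP administration on-site (all subjects" with no observation step. Table 1 has none either. After that visit, SC IP is self-administered outside the clinic (3.1).

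**The concern.** A rule that observes only the first study injection works as a first-exposure precaution when that injection contains the drug. Here it does for the two evolocumab groups and does not for the two ezetimibe groups. Their first antibody dose comes about 12 weeks later.

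SAP 10.6.1 tabulates injection site reactions and hypersensitivity or allergic reactions as events associated with injectable protein therapies, so the plan itself treats such reactions as relevant. The placebo run-in (7.2.1) and 12 weeks of placebo injections test tolerance of the injection and the device. Exclusion 224 removes known sensitivity or intolerance. Neither addresses a first reaction to the antibody. The stake is subject safety at one dose.

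**Working it through.** **1. How many subjects.** The allocation is 2:2:1:1 (Protocol 5.1) and the planned total is 60 (3.3).

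- Ezetimibe subjects: 60 × (1 + 1) / (2 + 2 + 1 + 1) = 20, that is 10 QM and 10 Q2W. This reproduces the 20 in Protocol 10.2.
- Share of the trial: 20 / 60 = 33%.
- Protocol 10.2 plans on "Assuming 5% of randomized subjects do not receive any IP": 20 × 0.95 = 19 dosed.
- The documents give no dropout rate. Assuming 0% to 10% of the dosed leave before Week 12: 19 × 1.00 = 19 and 19 × 0.90 = 17.1, so about 17 to 19.

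**2. Which dose is the first evolocumab dose.** The protocol does not say outright whether the Week 12 injection is blinded or open label. Three things bear on it.

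- Oral IP ends at the Week 12 visit and all subjects are injected on site there (7.2.3.7).
- SAP Appendix B ends the Week 12 lipid window at "min(91, first dose date of OLE"). Week 12 is Day 7 × 12 + 1 = 85, with a visit window of Days 82 to 88. If open label began at the next home dose, the scheduled days would be 99 (Week 14, Q2W) or 113 (Week 16, QM). Using the glossary windows (Q2W ± 3 days, QM ± 7 days), the earliest dates would be 82 + 14 − 3 = Day 93 and 82 + 28 − 7 = Day 103. Both are after Day 91, so with on-schedule dosing the extension date could never be the minimum. It can be if open label starts at Week 12.
- The blinded-period exposure formulas in SAP 6.3 fit the same reading. A last blinded Q2W dose at Week 10 gives Day 71 + 14 = 85, and a last blinded QM dose at Week 8 gives Day 57 + 28 = 85. This is compatible with a Week 12 switch but does not prove it.

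Week 12 is the better reading. On the other reading the first evolocumab dose is self-administered away from the clinic, also with no stated observation.

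**3. Whether anything else keeps the subject in the clinic.** Section 6.2.1.1 makes the injection the last procedure at on-site visits, so no later procedure fills the gap.

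**4. Cost of observing everyone once.** 60 × 0.5 h = 30 subject-hours. With 57 dosed (60 × 0.95), 57 × 0.5 h = 28.5 subject-hours.

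**The case against.** The strongest points on the other side are these.

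- **Purpose is inferred.** Section 6.2.1.1 gives no reason for the 30 minutes and applies them to placebo as well as evolocumab, so general supervision of injection technique would fit. This stands as a caveat. However, applying the rule to placebo is also what blinding requires, so it does not show that antibody exposure was not the reason.
- **Unseen documents.** Administration details are delegated to the IPIM, and the dosing schema is a figure that could not be seen. This stands: what is shown is that the protocol is silent.
- **Deliberate and partly mitigated.** Amendment 3 narrowed the rule on purpose, the Week 12 dose is given with staff present, and a data monitoring committee reviews safety. All true. The stated rationale does not mention the switch from placebo to evolocumab, and what is missing is a stated period rather than supervision.
- **The number actually affected may be smaller.** The superseded text, cited only as history, required observation at each dosing visit. Amendment 3 is dated 21 March 2017, and the primary analysis used a cut-off of 02 November 2017 with every continuing subject past Week 24. The last Week 12 visits were therefore about 84 days earlier, near 10 August 2017. Only subjects reaching Week 12 between site adoption of the amendment and that date fall under the narrowed rule. Enrolment dates are not given, so the realised number could lie anywhere from 0 to 20.
- **Timing.** SAP 10.1 describes the primary analysis as completed, so in this trial the switch has passed. The point concerns the protocol as written.
- **The switch date is not confirmed.** Protocol 3.1 places open-label evolocumab after the Week 12 visit. Read literally, that puts the first dose at home, which enlarges the gap. It does mean the fix should be tied to the first open-label injection and not to the visit label alone.

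**Conclusion.** The concern holds. As written, the protocol requires observation after first antibody exposure for the evolocumab groups and states none for the ezetimibe groups. The upper bound is 20 of 60 planned subjects (33%), 19 after the planned 5% not dosed, and about 17 to 19 under an assumed 0% to 10% loss before Week 12.

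The conclusion rests on the protocol text alone and would fall away in substance if the IPIM already requires observation at the switch. Week 12 as the switch visit is a well-supported inference, not a stated fact. The size of the safety benefit is unknown because the documents give no hypersensitivity rate. No endpoint, power figure or efficacy analysis changes. This is a modest, inexpensive safety improvement that should be made.

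**What to change.** Extend 6.2.1.1 so that the minimum 30-minute observation also follows each subject's first open-label SC injection, and state that this injection is given on site at Week 12. Add a matching bullet to 7.2.3.7. Wording the rule around the first open-label injection also makes clear that it still applies to someone who misses the Week 12 dose.

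Apply it to all subjects, not only those who had placebo. Protocol 10.4.2 places the primary analysis after Week 24, and only then "the study will also be unblinded". Observing everyone reveals no allocation. If the IPIM already contains the instruction, a cross-reference in 6.2.1.1 is enough.

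The text change is one clause and one bullet. The burden is one 30-minute wait per subject, at most 30 subject-hours, at a visit already held on site. As a stand-alone amendment it would also need investigator agreement and IRB/IEC approval (12.1) across approximately 40 sites (3.2), so it is cheapest when carried in an amendment made for other reasons.
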